5 STUDY POPULATION SELECTION

5.1 Study Population

Patients who have completed all study requirements in Study-HGT-SAN-055 and who elected to continue HGT-1410 treatment will be eligible to participate; a maximum of 12 patients are planned for this study.

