10 PLANNED STATISTICAL METHODS

10.1 General Statistical Methodology

This is an open-label extension of study HGT-SAN-055 to evaluate the long-term safety and clinical outcomes of intrathecal administration of HGT-1410 in patients with MPS IIIA. The statistical methodology supporting the trial will focus on descriptive rather than inferential approaches, given the early phase and objectives of this trial.

Data will be summarized by dose group (10 mg, 45 mg, and 90 mg) with respect to demographic and baseline characteristics, efficacy variables, and safety variables. Summary statistics for continuous variables will include the n, mean, standard deviation, median, minimum and maximum. Categorical variables will be summarized in a contingency table by the frequency and percentage of patients in each category. Data will be plotted to assess trends across time as appropriate.

No a priori hypotheses will be tested. Exploratory hypotheses may emerge from the data analysis, in which case, appropriate testing methods will be applied and specified in the statistical analysis plan.

There are no formal hypotheses associated with the evaluation of the safety and performance of the IDDD device (SOPH-A-PORT Mini S). All analyses of device safety and performance will be descriptive and no statistical testing will be performed. Device related analyses will be based on patients for whom the device implant procedure was performed and are described in the sections below.

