10.6 Efficacy, Safety, and Pharmacodynamic Evaluations

10.6.1 Primary Analyses

10.6.1.1 Safety Analysis

In general, safety assessments will be based on all assessments post-baseline. The assessment of safety will be based primarily on the frequency of AEs, and on the frequency of clinically notable abnormal vital sign and laboratory values. Changes from baseline will be calculated by subtracting the baseline value from the post-baseline value.

All enrolled patients who had an IDDD surgical procedure and/or received administration of HGT-1410 will be included in the safety analysis.

Adverse events will be recorded throughout the study and at early termination. Adverse events and medical conditions will be coded using the Medical Dictionary for Regulatory Activities (MedDRA).

Adverse events will be summarized by presenting, for each dose group, the number and percentage of patients having any AE, having an AE in system organ class, and having each individual AE. In addition, those events which resulted in death or were otherwise classified as serious will be presented in a separate listing. The incidence of treatment-emergent adverse events, defined as all AEs from the time of the surgery for IDDD implantation to the last follow up contact, ie, 30 days after the last HGT-1410 administration, (new or worsened from baseline) will be summarized by system organ class, severity, type of adverse event and relationship to trial medication/procedure.

Treatment-emergent AEs deemed related to HGT-1410 administration will be summarized separately.

IDDD and procedure-related AEs will be summarized within system organ class by preferred term. IDDD and procedure-related AEs will be tabulated by severity (mild, moderate, severe) and degree of relatedness. Separate tabulations will be provided for adverse events related to the IDDD, device surgical procedure (including post-implant infections) and IT administration process. These summaries will be presented by device and overall, as appropriate.

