Descriptive summaries of clinical laboratory evaluations (hematology, serum chemistry, urinalysis and CSF) results will be presented in summary tables by evaluation visit. Changes from baseline will be summarized for each post-baseline visit. Each laboratory result will be categorized as a patient having had (1) an Abnormal and Clinically Significant (CS) value at any time, (2) no CS values at any time but had at least one Abnormal and not CS (NCS) value, and (3) no CS or NCS values at any time; the number and percentage in each category will be presented. For any patient who experiences a CS laboratory result at any time that was not CS at

baseline (or the most recent non-missing value prior to the start of the treatment), their entire profile for that particular laboratory parameter will be presented as a listing.

The observed values and changes from baseline for vital sign data will be summarized for each dose group. Shift tables may be presented, utilizing reference ranges. Patients with notably abnormal values will be identified and listed separately along with their values.

The observed values and changes from baseline for ECG data will be summarized for each dose group. Patients with any clinically significant findings and/or conduction abnormalities will be listed separately along with their values.

Anti-rhHNS antibody formation will be monitored throughout the study. Results will be presented in summary tables by number and percentage of positive and negative specimens by evaluation visit, and number and percentage of positive and negative specimens overall. The effect of antibodies on other safety parameters will be assessed by presenting summary tables by antibody status.

For those patients who fail to complete the study, the reason for discontinuation will be listed by patient and dose group.

Listings of all study safety data will be presented.

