Appendix 1 Schedule of Events

Table A1-1 HGT-SAN-067 Study Assessments for Patients Who Have Received 6 Months of HGT-1410 Treatment in Study HGT-SAN-055

Assessment	Screening/or HGT-SAN-055 EOS Visit ^j (Month 6 from the start of HGT-SAN-055)	Month 7 through Month 80 (from the start of HGT-SAN-055)					
		Dosed every 28 (±7) days (ie, Q4W)		Months 12, 24, 36, 54, 60, 72 and 78 (from the start of HGT-SAN-055)	Months 9, 15, 18, 21, 27, 30, 33, 39, 42, 45, 48, and 51 (from the start of HGT-SAN-055)	EOS ^c Month 79 (from the start of HGT-SAN-055)	Month 80 Safety Follow-up ^f
Pre-Tx Day 1 ^a	IT dosing Day 2 (±2)						
Informed Consent/Enrollment		•		• ^r			
Physical Examination	•	• ^p	• ^p	• ^p			
Symptom-Directed Physical Examination		• ^p	• ^p			•	
Neurological Examination ^h	•	•	•			•	
Height and Weight	•	•				•	
Head Circumference	•			•		•	
Visual and Hearing Assessment				•		•	
ECG	•		• ^b				
Vital Signs	•	•	•			•	
Hematology	•	•				•	
Serum Chemistry	•	•				•	
anti-rhHNS antibody testing (serum) ^k	•			•		•	
Plasma storage for biomarkers	•	•		•		•	
Pregnancy Testing ^l	•	•				•	
Urinalysis	•	•				•	
Urine GAGS	•			• ^e		•	
Leukocyte pellet preparation ^m	•						
CSF chemistry and cell counts ^c	•	•				•	
CSF sample storage ^{c,o}	•	•				•	
CSF Heparan Sulfate and Heparan Sulfate Derivatives ^c	•			•	•		
Anti-rhHNS antibody testing (CSF) ^c	•			•		•	

Table A1-1 HGT-SAN-067 Study Assessments for Patients Who Have Received 6 Months of HGT-1410 Treatment in Study HGT-SAN-055

Assessment	Screening/or HGT-SAN-055 EOS Visit ^j (Month 6 from the start of HGT-SAN-055)	Month 7 through Month 80 (from the start of HGT-SAN-055)					
		Dosed every 28 (±7) days (ie, Q4W)		Months 12, 24, 36, 54, 60, 72 and 78 (from the start of HGT-SAN-055)	Months 9, 15, 18, 21, 27, 30, 33, 39, 42, 45, 48, and 51 (from the start of HGT-SAN-055)	EOS ^c Month 79 (from the start of HGT-SAN-055)	Month 80 Safety Follow-up ^f
		Pre-Tx Day 1 ^a	IT dosing Day 2 (±2)				
Auditory Brainstem Response (ABR) ^q	•			•			
MRI of the Head	•			•		• ⁿ	
HGT-1410 dosing: every 28 (±7) days ^{d, g, .}			•				
Full Neurodevelopmental Testing ⁱ	•			•		•	
Children's Sleep Habits Rating Scale	•			•		•	
Child Health Questionnaire-50	•			•		•	
Child Health Questionnaire-87	•			•		•	
Infant Toddler QOL Questionnaire	•			•		•	
Concomitant Medications, Therapies, and Procedures	•	•	•			•	•
Adverse Event Monitoring	•	•	•			•	•

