3 STUDY ENDPOINTS

3.1 Primary Endpoint

The primary endpoints of this study are related to the long-term safety of intrathecal HGT-1410 administration. The safety endpoints are:

[figure not shown]
- adverse events (type and severity)
- changes in clinical laboratory testing (serum chemistry including liver function tests, hematology, and urinalysis)
- electrocardiograms (ECG)
- CSF chemistries (including cell counts and inflammatory markers)
- anti-rhHNS antibodies (in CSF and serum).

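### The overall antibody summary counts positive specimens, so it does not show how many patients ever became, or newly became, anti-rhHNS positive

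*Protocol*

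**What the plan says.** Section 3.1 lists "anti-rhHNS antibodies (in CSF and serum") among the primary safety endpoints, and the Amendment 7 version of Section 3.1 keeps it.

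Section 10.6.1.1, which is available only in its Amendment 6 form, says the results will be presented as the "number and percentage of positive and negative specimens by evaluation visit, and number and percentage of positive and negative specimens overall". The only other antibody analysis in that section is "The effect of antibodies on other safety parameters will be assessed by presenting summary tables by antibody status". Section 10.6.3.2 adds that changes in CSF biomarkers may be tabulated the same way. Antibody status is not defined in either place.

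Elsewhere the unit is the patient:

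- Section 10.1, general rule: "Categorical variables will be summarized in a contingency table by the frequency and percentage of patients in each category".
- Section 10.6.1.1, adverse events: "for each dose group, the number and percentage of patients having any AE".
- Section 10.6.1.1, laboratory results: "Each laboratory result will be categorized as a patient having had (1) an Abnormal and Clinically Significant (CS) value at any time".
- Section 10.6.2.1, device failures and malfunctions: the proportion of patients with at least one.

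**The concern.** Each child is tested repeatedly over several years, and children who leave are not replaced (Section 7.26). A percentage taken over all specimens gives more weight to children who stay longer. It also dilutes a late converter with that child's own earlier negative results. It is the only summary the section names that spans all visits, so it is the figure likely to be read as the antibody rate.

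With "a maximum of 12 patients are planned for this study", the natural safety question is how many children made antibodies and how many of those were new on treatment. The overall line answers neither, and two dose groups with the same antibody incidence could show different percentages merely because their follow-up differed. One child in 12 is 1/12 = 8.3 percentage points, so the choice of unit is not a rounding matter.

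**Working it through.** The protocol gives no antibody rate, so there is no stated figure to reproduce. The check is a direct count.

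**Inputs from the protocol**

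- Patients: at most 12 (Section 5.1).
- Sampling, Table A1-1 (Amendment 6): the screening column (Month 6), "Months 12, 24, 36, 54, 60, 72 and 78 (from the start of HGT-SAN-055"), and the end-of-study visit (Month 79). That is 1 + 7 + 1 = 9 specimens per matrix for a completer, or 12 × 9 = 108 for 12 completers.
- Sampling, Section 8.2.1.1: Month 66 is also listed, giving 10 per completer and 120 in total.

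**Assumptions, for illustration only**

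All 12 places are filled, one matrix is counted (serum), positivity persists once it appears, and conversion and exit dates are as stated in each case.

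**Formulas**

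- Specimen percentage = positive specimens / all specimens.
- Patient percentage = patients ever positive / patients tested.

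**Same specimen figure, different numbers of patients (Table A1-1)**

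- 3 of 12 positive from Month 12: 8 of 9 specimens each, 3 × 8 = 24; 24/108 = 22.2%. Patients: 3/12 = 25%.
- 12 of 12 positive from Month 78: 2 of 9 specimens each, 12 × 2 = 24; 24/108 = 22.2%. Patients: 12/12 = 100%.

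**Same number of patients, different specimen figures (Table A1-1; 6/12 = 50% of patients throughout)**

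- Conversion at Month 12, all complete: 6 × 8 = 48; 48/108 = 44.4%.
- Conversion at Month 78, all complete: 6 × 2 = 12; 12/108 = 11.1%.
- Conversion at Month 12, the six converters then leave with no further sample: 6 × 1 = 6 positive out of 6 × 2 + 6 × 9 = 66; 6/66 = 9.1%. If each leaver gives one exit sample, which Section 8.3 requests but leaves voluntary, it is 12/72 = 16.7%.

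**Section 8.2.1.1 schedule (10 specimens per completer)**

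- 3 of 12 positive from Month 12: 27/120 = 22.5%. 12 of 12 positive from Month 78: 24/120 = 20.0%.
- With 6 of 12 ever positive, the range is 6/72 = 8.3% (converters leave after Month 12) to 54/120 = 45.0% (conversion at Month 12, all complete).

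The two schedules differ on Month 66, but the result does not turn on which one applies.

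**By-visit line**

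With one specimen per child per matrix at a visit, specimens positive / specimens equals patients positive / patients tested at that visit. That line is sound. It still does not give the number ever positive, because children positive at different visits, or who have left, are not accumulated.

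**The case against.** The strongest reply is that patient-level information is not shut out. The same sentence plans by-visit percentages, which are in effect patient percentages. Tables by antibody status require children to be classified somehow. Section 10.6.1.1 promises listings of all safety data, and with at most 12 children a reader could count from them. Section 10.6.4 leaves the final presentations to the SAP, which is not shown. The study tests no hypotheses, and safety is to be judged mainly on adverse events and on abnormal vital signs and laboratory values.

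Much of this stands. A reader might infer that the trial will be unable to say how many children made antibodies. The documents do not support that, because the count can be recovered from the listings. A reader might also infer that serum and CSF results will be pooled. The protocol does not say so: the two have separate sections (7.7.4 and 7.7.6.3) and separate rows in Table A1-1. Finer definitions, such as persistent against transient positivity, are ordinary SAP content, and their absence is no fault.

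What the reply does not remove is that the protocol itself fixes the specimen as the unit of the overall summary of a primary endpoint, against its own general rule. A listing that lets the reader count is not a planned summary, and an undefined antibody status with no count attached does not fill the gap.

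**Conclusion.** The point holds for the overall line only. That percentage does not identify the number of patients ever or newly positive: in the illustration 22.2% of specimens corresponds to 25% or to 100% of patients, and 50% of patients corresponds to anything from 9.1% to 44.4% of specimens. These sizes rest on assumed conversion and exit dates, 12 patients and persistent positivity. They show what the summary can do, not what the data will show.

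The by-visit percentages are not at fault, provided there is one specimen per matrix per visit. Whether the wording survives in Amendment 7 cannot be checked, since its Section 10 is not shown. The flaw is one of reporting, worth correcting because the endpoint is primary and the correction is nearly free. It does not threaten the data.

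**What to change.** In Section 10.6.1.1, replace the overall specimen line with two patient counts, by dose group and separately for serum and CSF, with patients tested as the denominator:

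1. number and percentage of patients ever positive;
2. number and percentage of patients negative at the protocol's baseline (the first HGT-SAN-055 dose) who later become positive.

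Use this classification to define antibody status for the tables in Sections 10.6.1.1 and 10.6.3.2. Keep the by-visit table. The split into persistent and transient positivity can be left to the SAP.

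The cost is one sentence and one table, with no new data. The second count uses the baseline antibody result from HGT-SAN-055, whose own schedule is not in this document; it is assumed to be available, as it must be for other changes measured from that baseline.

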10.6.2 Other Observations Related to Safety

10.6.2.1 IDDD Performance

IDDD safety and performance will be summarized in detail for patients implanted with the SOPH-A-PORT Mini S. Difficulties associated with the implant procedure (e.g. excessive bleeding, CSF leakage, etc.) will be summarized. A summary of abnormal findings from the IDDD radiological assessments will also be presented.

The proportion of patients with at least one IDDD failure and/or malfunction, as well as the number of and reasons for IDDD failures/malfunctions will be summarized. The rate of IDDD failures/malfunctions and 95% confidence interval will also be estimated. The time from initial implant surgery to first IDDD failure and/or malfunction will be summarized. Patients without an IDDD failure/malfunction will be censored at their last study drug injection date. A by-patient listing of the device failure/malfunction data will be displayed.

The proportion of patients for whom a successful first injection of study drug occurred will be reported among those for whom a first injection was attempted (i.e. those who had an apparently successful implantation and did not suffer a device removal or revision prior to first scheduled injection). The proportion of patients who had no failed injection attempts during the study will also be summarized. The corresponding 95% confidence intervals of the proportion of interest will be estimated, where appropriate. Injections not given for patient reasons (e.g. patient uncooperative, competing medical issue, etc) will not be included in the determination of these success proportions.

10.6.3 Secondary Analysis

10.6.3.1 Clinical Assessments

The change from baseline in neurocognitive assessment based scores will be examined by dose group. Furthermore, the effect of HGT-1410 administration on QoL measures will be examined by presenting mean change from baseline by dose groups. Other relevant assessments which might help in the understanding of clinical activity will also be analyzed.

10.6.3.2 Pharmacodynamic Analyses

To determine the effects of HGT-1410 administration on biomarkers, mean change from baseline will be assessed at selected time points. The heparan sulfate reduction (in CSF) will be examined using mean change and the corresponding 95% confidence interval. Other exploratory biomarkers in CSF, serum, and urine may also be examined.

The effect of anti- rhHNS antibodies on the changes in CSF biomarkers may also be examined by presenting summary tables by antibody status.

10.6.4 Interim Analysis

No formal analysis or interim statistical testing for early stopping of the trial is planned. Descriptive analyses of the data before trial completion may be performed for safety monitoring, regulatory reporting, or general planning purposes.

The planned final analyses and presentations will be defined in the Statistical Analysis Plan (SAP).

11 ADMINISTRATIVE CONSIDERATIONS

11.1 Investigators and Study Administrative Structure

Before initiation of the study, the Investigators must provide the Sponsor with a completed Form FDA 1572 or Investigator Agreement. Study medications may be administered only under the supervision of the Investigators listed on this form. Curriculum vitae must be provided for the Investigators and sub-investigators listed on Form FDA 1572 or Investigator Agreement.

The Investigator should ensure that all persons assisting with the study are adequately informed about the protocol, any amendments to the protocol, the study treatments, and their study related duties and functions. The Investigator must maintain a list of sub-investigators and other appropriately qualified persons to whom he or she has delegated significant study related duties.

11.2 Institutional Review Board or Independent Ethics Committee Approval

Before initiation of the study, the Investigator must provide the Sponsor with a copy of the written IRB or IEC approval of the protocol and the informed consent form. This approval must refer to the informed consent form and to the study title, study number, and version and date of issue of the study protocol, as given by the Sponsor on the cover page of the protocol.

Status reports must be submitted to the IRB/IEC at least once per year. The IRB/IEC must be notified of completion of the study. Within 3 months of study completion or termination, a final report must be provided to the IRB/IEC. A copy of these reports will be sent to the study clinical monitor. The Investigators must maintain an accurate and complete record of all submissions made to the IRB/IEC, including a list of all reports and documents submitted. AEs which are reported to the US FDA or other Regulatory agencies (Investigational New Drug [IND] Safety Reports) must be submitted promptly to the IRB/IEC.

11.3 Ethical Conduct of the Study

The procedures set out in this study protocol, pertaining to the conduct, evaluation, and documentation of this study, are designed to ensure that the Sponsor and Investigators abide by good clinical practice (GCP) as described in the 21 CFR Parts 50, 56, and 312 and the International Conference on Harmonization (ICH) GCP Guidelines.

11.4 Patient Information and Consent

Before enrolling in the clinical study, the patient's parent(s), or the patient's legally authorized representative(s) must consent to participate after the nature, scope, and possible consequences of the clinical study have been explained in a form understandable to him or her. An informed consent form that includes information about the study will be prepared and given to the patient's parent(s), or the patient's legally authorized representative(s). This document will contain all FDA and ICH-required elements.

The informed consent form must be in a language understandable to the patient's parent(s), or the patient's legally authorized representative(s) and must specify who informed the patient's parent(s) or the patient's legally authorized representative.

After reading the informed consent document, the patient, patient's parent(s), or the patient's legally authorized representative(s) must give consent in writing. The patient's consent must be confirmed at the time of consent by the personally dated signature of the patient, patient's parent(s) or the patient's legally authorized representative(s) and by the personally dated signature of the person conducting the informed consent discussions. If the patient, patient's parent(s), or the patient's legally authorized representative(s) is unable to read, oral presentation and explanation of the written informed consent form and information to be supplied must take place in the presence of an impartial witness. Consent (or assent) must be confirmed at the time of consent orally and by the personally dated signature of the patient, patient's parent(s) or by the patient's legally authorized representative(s). The witness and the person conducting the informed consent discussions must also sign and personally date the informed consent document. It should also be recorded and dated in the source document that consent was given.

A copy of the signed and dated consent document(s) must be given to the patient's parent(s), or the patient's legally authorized representative(s). The original signed and dated consent document will be retained by the Investigator.

The Investigator will not undertake any measures specifically required solely for the clinical study until valid consent has been obtained.

A model of the informed consent form to be used in this study will be provided to the sites separately from this protocol.

Where applicable, signed assent(s) to participate in the study must be obtained.

